#### Methods of evaluation

4

#### 4.1 Assessment of residual astigmatism

Measurement of residual astigmatism will be derived from autorefraction with an autorefractor (Topcon) with mean reading of 5 consecutive measurements in IOL mode, a subjective refraction by an optometrist using trial lenses and the cross cylinder method. All these measurements are non-invasive, non-contact and readily used in daily clinical practice.

# 4.2 Assessment of corneal astigmatism

Measurement of corneal astigmatism before and after surgery will be performed using the autokeratometry function of the IOL-Master (Zeiss) and the Scheimpflug technique

(Pentacam, Oculus). In the latter case, the simulated K-readings of the central 4 mm zone will be used.

# 4.3 Assessment of visual acuity

Measurement of uncorrected and best corrected visual acuity will be done using a back-lit EDTRS chart placed at 4m.

Near and distance unaided and corrected visual acuity will be measured

Reading speed, reading acuity and ciritical print size monocularly (Salzburg Reading Desk)

The Salzburg Reading Desk (SRD) is the prototype of a reading chart that measures reading speed and reading distance. Contrast and light conditions are preset and reading distance (+/- 0.2 cm), reading speed and their changes during the examination are measured. This ensures an objective evaluation of measurements under the same conditions at every follow-up.

Contrast vision under photopic and mesopic conditions (Pelli-Robson Chart)

#### Glare testing monocularly by Ogas:

The OQAS system consists of laser diagnostic sensory equipment, a computer workstation and custom designed software. It works by sending in an infrared light source and directly measuring the point spread function (PSF) of the optical system of the eye. Because OQAS measures all light reflected back off the retina, the measurement contains the effects of light scatter and all high order abrrations.

Dysphotopsia and satisfaction questionnaire – comparing the visual quality of the eyes as assessed under different conditions – to be filled in by patients at home shortly before the 3 months follow-up (see attachment)

# 4.4 Assessment of IOL position and rotation

IOL axis measurements are assessed from photos attained with a high-resolution digital retroillumination imaging system. The optical system consists of a Zeiss 120 slit-lamp for observation and imaging. A Zeiss retrolux illumination module is supplied with illumination provided by a Zeiss anterior segment flashpack through a fiber optic cable. For image acquisition we use a colour digital camera (Canon D5). The main advantage of this camera is the high light sensitivity of the large CCD chip, resulting in a high signal-to-noise ratio in the

acquired images. The images are directly transferred to a personal computer and saved to hard-disc. The images are assessed using a dedicated analysis software.

The axis marks are identified with a cursor and the axis of the IOL is registered. In order to ensure consistent alignment of the patient's head at each follow-up, the patient's head will be positioned as straight as possible according to the examiners subjective impression. A pilot

	А	В	С	D
	Excellent	Good	Average	Poor
Distance VA	0.0 or better	<0.0 to 0.18	<0.18 to 0.30	<0.30
(log mar)	ie. 6/6 or better	ie. 6/6 to 6/9	ie. <6/9 to 6/12	ie. <6/12
Near VA	N5 or better	<n5 td="" ton6<=""><n6 n8<="" td="" to=""><n 8<="" td=""></n>	</n6>	</n5>	<n6 n8<="" td="" to=""><n 8<="" td=""></n>	</n6>	<n 8<="" td=""></n>

study has shown this to be reproducible to about 2° concerning axis documentation.

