The new multifocal toric lenses combine the separate optical features of a standard multifocal lens and the toric lens to provide a superior multifocal outcome with precise and sustainable toric correction.

The alternative method to reduce corneal astigmatism as part of cataract surgery is to make relaxing incisions (cuts) on the steeper axis of the cornea. This technique is in use since more than 2 decades

and is widely used in clinical routine(5). As with toric IOLs, precise alignment of the cuts with the axis of astigmatism is essential. Nomograms for these astigmatism correcting incisions are available depending on the extent and the orientation of astigmatism and the age of the patient. The disadvantage of the incisional techniques is the variability of the effect between patients since it depends on factors such as the extent of scarring of the cuts after surgery as well as corneal thickness and shape. Also, there is a tendency for regression of the effect during the first 9 months after surgery. Furthermore there is a risk of infection of the corneal incision and microbial keratitis after limbal relaxing incision has been described. The main advantage is only the low cost.

Concerning alignment, the axis is defined by either corneal keratometry or topography, or both. Misalignments may be caused intra- or postoperatively. Intraoperatively, misalignment may happen due to cyclotorsion of the eye in the lying position or due to local anaesthesia, and due to imprecision of positioning of the IOL in the bag or of placing the astigmatism correcting incisions on the cornea. These imprecisions can be dealt with by preoperative marking of the eye in the sitting position and use of meticulous positioning of the IOL or incisions during surgery.

A Rayner single-piece open-loop IOL made of hydrophilic acrylate was shown to have a good haptic memory and is thought to adhere to the capsule resulting in little to no rotation after surgery. A toric optic design has been added to this multifocal IOL design.

One of the front and back surfaces of the lens defines a toric surface for an astigmatic optical correction, and one of the front and back surfaces, which can be the same surface or the opposite surface, defines a multifocal surface for a presbyopic optical correction, to provide visual acuity for astigmatic presbyopes

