#### 3.5 Variables and schedule of observations

#### 3.5.1 Outcome variables

Main outcome variables	•	
 
Composite scoring of unaided distance and near vision (monocularly and binocularly)
 
		
	•	Residual astigmatism evaluation by Subjective Refraction and autorefraction (Topcon) and		
	•	Any intraoperative or postoperative complications		

Additional outcome	Simulated K-readings using corneal topography (Pentacam)			
variables	Rotational stability of the IOL - angle of axis as measured from retroillumination photographs: Orientation [degrees]			
	
 
Dysphototpsia and satisfaction questionnaire - monocularly
 
			

- Reading speed Salzburg reading test monocularly
- Glare testing (Oqas)– monocularly
- Post-operative dominance will be established using the visual acuity results to ensure that there are equal numbers of dominant and non-dominant eyes in both groups

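### Section 4.4 reads the lens axis against a head position judged by eye, so tilt or torsion between visits counts as lens rotation; the 2 degree reproducibility figure is undefined

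*Protocol*

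**What the plan says.** Section 3.5.1 lists among the additional outcomes "Rotational stability of the IOL - angle of axis as measured from retroillumination photographs", in degrees. The follow-up table in section 3.4.1 schedules the photographs on the operation day (after 1 hour), at 1 month and at 3 months.

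Section 4.4 gives the reading method. "The axis marks are identified with a cursor and the axis of the IOL is registered". To keep visits comparable, the head is to be "positioned as straight as possible according to the examiners subjective impression". A pilot "study has shown this to be reproducible to about 2° concerning axis documentation". On processing, the section says only this: "The images are assessed using a dedicated analysis software". It names no landmark in the eye and describes no correction for tilt.

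Section 1.1 says that the lens design "is thought to adhere to the capsule resulting in little to no rotation after surgery". Section 4.6.1 limits the analysis of outcome variables to descriptive statistics.

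**The concern.** Rotation is the difference between two axis readings taken weeks or months apart. If the camera frame is the reference and the head is set upright by eye, any change in head tilt or eye torsion between the two photographs enters that difference degree for degree. The photograph then offers no means of separating it from movement of the lens in the capsular bag.

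This matters because the expected signal is close to zero. Stability is usually judged by the size of the change, its spread, or the share of eyes beyond some limit, and random reading error inflates all three. Section 4.7 says that the findings will be published and used to power a full-scale trial, so a descriptive figure for rotation should be one that a reader can interpret.

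**Working it through.** **Inputs**

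- Reproducibility of about 2 degrees (section 4.4). This is a pilot result given without its data, so it cannot be reproduced. Its statistical meaning is not stated.
- Rotation as a difference of two readings (photograph schedule, section 3.4.1).
- 30 toric eyes: 30 patients (section 3.2.1), one toric eye each by design.
- Assumptions of this check: errors are normal, unbiased and independent between visits.

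**What the reading contains.** Write the recorded axis at visit t as A(t) = L(t) + T(t) + e(t). Here L is the lens axis within the eye, T is the tilt of the eye in the camera frame (head position plus torsion), and e is cursor error. Between visits 1 and 3:

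A(3) − A(1) = [L(3) − L(1)] + [T(3) − T(1)] + [e(3) − e(1)].

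For a still lens the first bracket is 0 and the other two remain. If a fixed feature of the eye is also read, as K + T(t) + f(t), where K is its constant direction and f its own reading error, then subtracting it removes T and brings in f. The landmark therefore helps when tilt and torsion vary more than the landmark reading does.

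**Apparent rotation of a still lens.** For a zero-mean normal difference with standard deviation SD_diff, the mean absolute value is SD_diff × √(2/π) = SD_diff × 0.798. A single-reading SD is multiplied by √2 to give SD_diff.

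| Meaning given to 2 degrees | SD_diff | Mean absolute rotation |
|---|---|---|
| 95% limit of a difference | 2/1.96 = 1.02 | 0.81 |
| 95% limit of one reading | 1.02 × √2 = 1.44 | 1.15 |
| SD of a difference | 2.00 | 1.60 |
| SD of one reading | 2 × √2 = 2.83 | 2.26 |

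Two further meanings are possible. If 2 degrees is the mean absolute difference, the answer is 2.0 directly. If it is the mean absolute error of one reading, the answer is 2 × √2 = 2.8, just above the range quoted here.

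**Signed mean.** The expected value is 0 under every meaning. Its standard error in 30 eyes is SD_diff/√30, which runs from 1.02/5.48 = 0.19 to 2.83/5.48 = 0.52 degrees.

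**Still lenses that would look rotated.** The cut-offs are illustrative; the protocol sets none.

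| SD_diff | Beyond 3 degrees | Beyond 5 degrees |
|---|---|---|
| 1.02 | 0.3% | about 0% |
| 2.00 | 13% | 1% |
| 2.83 | 29% | 8% |

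In 30 eyes the 3 degree column comes to about 0, 4 and 9 eyes.

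**When the lens does move.** Over SD_diff of 1.02 to 2.83, a true rotation of 2 degrees would read on average 2.0 to 2.8 in absolute value, and a true 5 degrees would read 5.0 to 5.1. The inflation is confined to small rotations, which are the ones that the protocol expects.

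**The case against.** The strongest reply is that the protocol discloses this limit. Section 4.4 states the positioning method and follows it with a pilot figure for its reproducibility. Nothing there is misstated or contradictory. That is right, and the point is an improvement of method. Disclosure does not remove the error, however, and an undefined figure does not let a reader subtract it.

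Three more objections stand in part:

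- **Choice of summary.** The upward bias belongs to absolute rotation, and the protocol does not say which summary it will use; that choice can be left to an analysis plan. A reader might infer that the mean rotation itself is off by 0.8 to 2.3 degrees. It is not: the signed mean has expectation 0. But clockwise and anticlockwise movements cancel in a signed mean, so it cannot describe stability alone.
- **Source of the error.** A reader might put the whole 2 degrees down to head tilt. The documents give no split between tilt, torsion and cursor error.
- **The software.** It is not described, so an internal reference cannot be ruled out. The only means of alignment that the text states is head placement.

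A reader might also infer that residual astigmatism in toric eyes would be wrongly blamed on rotation. The documents do not support this. Section 4.1 measures residual astigmatism by autorefraction and subjective refraction, independently of the photographs, and no planned analysis attributes it to lens rotation.

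**Conclusion.** The point holds as a low-cost improvement to an additional, descriptive outcome. On the method as written, tilt or torsion between visits cannot be told apart from lens rotation. A lens that does not move would show a mean absolute rotation of about 0.8 to 2.3 degrees, which can match or exceed the movement expected.

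The range depends on what the 2 degree figure means and on independent, unbiased normal errors. The share of it due to tilt and torsion is unknown. The main outcomes (composite acuity score, residual astigmatism and complications) do not use the axis photographs and are unaffected.

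**What to change.** In section 4.4:

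1. Where a fixed feature of the same eye (for example an iris or limbal-vessel landmark) is visible on the operation-day photograph, measure the axis marks relative to it at every visit.
2. Where none is visible, keep the present method, flag the eye, and show results by method so that the two are not mixed.
3. Report signed and absolute rotation, with the repeat-reading SD of the method used beside them. Re-reading one photograph captures reading error only, so for flagged eyes also give the pilot figure, which covers head placement.
4. State what the 2 degree figure is: SD, limit or other; one reading or a difference; and whether it includes cursor error.

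The cost is one extra reading per image, with no new visit or procedure. Whether the present software can take that reading is not described and should be confirmed. Some images will lack a usable landmark. The landmark reading has its own error, so its repeatability should be checked on images already taken before it is relied on.

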#### 4.5 Data handling procedures

A case record form will be completed for each patient. The entries will be checked by trained personnel and any errors or inconsistencies will be checked immediately.

#### 4.5.1 Data Management

All data will be entered into a specially designed ACCESS database by the Research Fellow. This database will be on the H drive of Moorfields Eye Hospital intranet and will be password protected and only accessible by authorised personnel.

#### 4.6 Biometric methods

#### 4.6.1 Biometric methods - outcome variables

The outcome variables will be assessed using descriptive statistics.

#### 4.6.2 Biometric methods - Adverse events/Safety investigations

All adverse events will be properly listed and an appropriate method will be used to summarise the data.

#### 4.7 Data Analysis and Use of study findings

We propose to generate a composite measure with 4 categories based on measures of distance and near visual acuity, but will use this pilot data (with patient questionnaire data) to determine how best to do this.

#### Components of the Visual Scoring System

The findings of this pilot study will be published by the investigators in a scientific journal and presented at scientific meetings, and will be used to power a full-scale randomised controlled trial.

# 4.8 Benefits and Risks

Patients will have the opportunity to take part in a project that offers them the chance to be spectacle independent. The risks to the patients above those of the surgery itself will come from intolerance of whichever treatment arm they are randomised to. These risks are low, The European study of diffractive IOLs found that 74.4% never wore spectacles, glare and haloes occurred in 8.5% and 4.2 % respectively and 95.7 % of patients said they would have the same implant again (2).

Where a patient is intolerant of the multifocal IOL they will be offered bilateral sequential IOL exchange with monofocal implants. Any further refractive surgery(7) required (e.g. residual bothersome astigmatism) will be performed if needed and after risks/benefit explanation and the costs will be met by the company sponsoring the trial (Rayner). In addition, Rayner Intraocular Lenses Ltd have agreed to supply all the lenses required for this trial free of charge and have agreed a small unrestricted grant of upto £5,000 to cover the costs of the study.

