### 1 Introduction

### 1.1 Background

Spectacle independence is a central aim in modern cataract surgery. Although bilateral monofocal IOL implantation, aiming for 0.00 to -0.50D, leads to high levels of patient satisfaction, spectacle dependence for reading and other near vision tasks is the usual result. Most surgeons faced with a patient with bilateral cataract would leave them either emmetropic or with very low levels of post-operative myopia in both eyes. This leaves most patients dependent on spectacles for near visual tasks.

One technique available to surgeons to reduce spectacle dependence is to use a multifocal IOL. Recent diffractive IOL designs have improved spectacle independence while reducing the glare phenomena(1)(6). A European study of the Restor diffractive IOL found that 74.4% never wore spectacles, glare and haloes occurred in 8.5% and 4.2% of patients respectively and 95.7% of patients said that they would have the same implant again(2). Only one patient out of 127 had the IOL explanted because of glare and haloes. FDA data for the Restor reported a spectacle independence figure of 80% (www.fda.gov/cdrh/pdf4/p040020.html). Bilateral implantation with contemporary multifocal lens implants reduce spectacle dependence and is well tolerated; but it involves compromise for the quality of distance vision. Residual astigmatism after cataract surgery can influence the post operative outcome and lead to poor performance of these lenses (3). Hence it is important to correct the astigmatism during cataract surgery to get the optimal result with Multifocal IOLs. The options available to correct astigmatism is either to implant a multifocal toric IOL or make limbal relaxing incisions combined with a multifocal IOL.

With increasing demands of patients concerning refractive outcome after cataract surgery, toric IOLs that correct corneal astigmatism have been introduced more widely to cataract surgery. Originally toric IOLs were used mainly for patients with high degrees of astigmatism, especially after corneal surgical procedures such as penetrating keratoplasties. Recently, toric IOLs are available from numerous manufacturers to correct lower amounts of astigmatism which are much more prevalent. This should result in less spectacle dependence of patients due to the precise nature of the astigmatic correction (4).

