# Extra trial visit

3-4 months after the second eye has been operated on.

Follow-up examinations are performed as depicted in the table:

Assessments/Examinations	Visit 0	Visit 1	Visit 2	Visit 3
	PreOp	Op day (after 1 hr)	1 month	3 months
Autorefractor	х		х	х
Subjective Refraction				х
Near, Distance VA			Х	х
IOL Master Keratometry	х		Х	х
Topography (Pentacam)	х		х	Х
Retroillumination photo		х	х	х
Slitlamp examination	х	Х	Х	Х
Dysphototpsia and satisfaction questionnaire				х
Reading speed(Salzburg reading test)				х
Contrast Vision(Pelli Robson chart)				х
Glare testing(oqas)				х

Postoperative standard medication: dexamethasone gtt, qid for 2 weeks and then bid for one week, chloramphenicol gtt qid for 2 weeks

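### Does the protocol lose a main outcome by scheduling subjective refraction and the questionnaire only at Visit 3, although further surgery is allowed without a time limit?

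*Protocol*

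**What the plan says.** Section 4.8 (Benefits and Risks) makes two commitments. For patients intolerant of the multifocal lens, "they will be offered bilateral sequential IOL exchange with monofocal implants". For other refractive problems, "Any further refractive surgery(7) required (e.g. residual bothersome astigmatism) will be performed if needed", after the risks and benefits have been explained and with the cost met by the sponsoring company. Neither commitment has a time point.

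In the visit table under Extra trial visit (section 3.4.1), subjective refraction and the dysphotopsia and satisfaction questionnaire each have one mark, at Visit 3 (3 months). The text on the questionnaire agrees: it is "to be filled in by patients at home shortly before the 3 months follow-up". The extra trial visit itself falls "3-4 months after the second eye has been operated on". Autorefraction and near and distance acuity are marked at both 1 month and 3 months.

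Section 3.5.1 lists three main outcomes: the composite of unaided distance and near vision, residual astigmatism, and complications. The entry for astigmatism names two methods: "Residual astigmatism evaluation by Subjective Refraction and autorefraction (Topcon)". The questionnaire is an additional outcome. Section 4.7 also gives it a part in building the composite: the investigators "will use this pilot data (with patient questionnaire data) to determine how best to do this".

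**The concern.** Residual astigmatism is a main outcome, and it is also the protocol's own example of a reason to operate again. If an eye is repaired before Visit 3, its only scheduled subjective refraction describes the repair and not the randomised treatment. The eyes affected would be those with the worst result, so the loss is related to the outcome and would tend to narrow the difference between treatments. A bilateral lens exchange would alter both eyes of a patient and with them the whole within-patient comparison. An intolerant patient's answers about the allocated lenses would also be missing from the data used to shape the composite.

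The window is not short. The second eye is to be listed within 3-4 weeks where possible. If Visit 3 is the extra trial visit 3-4 months after that, a first-operated eye waits roughly 4-5 months for its only subjective refraction. An analysis plan can decide how to treat a value taken after a repair, but it cannot recreate one that was never taken before it.

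**Working it through.** **What the text commits to.** Section 4.8 says that further surgery is available and who pays. It does not say that any procedure will take place before Visit 3. The visit table says when outcomes are measured. The two conflict only if early procedures are assumed, and that assumption comes from outside the protocol.

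**What is exposed if an eye is re-operated early.**

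| Measure | Role (3.5.1) | Scheduled before Visit 3? |
|---|---|---|
| Distance and near acuity | Components of the composite, a main outcome | Yes, 1 month |
| Autorefraction | One of two astigmatism methods, a main outcome | Yes, 1 month |
| Complications | Main outcome | No visit mark in the table; slit-lamp examination on the day of surgery and at 1 month |
| Subjective refraction | The other astigmatism method | No |
| Questionnaire | Additional outcome; informs the composite | No |

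For a procedure after the 1-month visit, the exposed measures among these are one of two astigmatism methods and the questionnaire. A procedure before 1 month would also precede the acuity and autorefraction readings.

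**Size, refractive repair.** The documents give no rate and no distribution, so every input here is an assumption except the 30 patients (section 3.2.1). Residual astigmatism follows a gamma distribution with coefficient of variation 0.6, so its shape is 1/0.6² = 2.78. Mean *m* is 0.4-0.5 D for toric eyes and 0.7-0.8 D for LRI eyes. A share *r* of eyes above 1.0 D is repaired to 0.25 D before Visit 3. The expected fall in an arm's mean is *r* × D, where D = E[X; X > 1] − 0.25 × P(X > 1).

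| *m* (D) | P(X > 1) | E[X; X > 1] | D |
|---|---|---|---|
| 0.4 | 0.024 | 0.028 | 0.022 |
| 0.5 | 0.068 | 0.083 | 0.066 |
| 0.7 | 0.204 | 0.276 | 0.225 |
| 0.8 | 0.280 | 0.396 | 0.326 |

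The shrinkage of the difference between treatments is *r* × (D for LRI − D for toric). With eyes independent, the standard error over 30 pairs is √[(0.6*m*₁)² + (0.6*m*₂)²]/√30.

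| Toric vs LRI (D) | Shrinkage at 2% / 5% / 10% (D) | SE (D) | Ratio at 10% |
|---|---|---|---|
| 0.4 vs 0.8 | 0.006 / 0.015 / 0.030 | 0.098 | 0.31 |
| 0.5 vs 0.8 | 0.005 / 0.013 / 0.026 | 0.103 | 0.25 |
| 0.4 vs 0.7 | 0.004 / 0.010 / 0.020 | 0.088 | 0.23 |
| 0.5 vs 0.7 | 0.003 / 0.008 / 0.016 | 0.094 | 0.17 |

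With a within-patient correlation of 0.3-0.5, the ratio at 10% runs from 0.20 to 0.40 across the four pairs. At *r* = 0 the shrinkage is zero. Expected LRI eyes repaired at 10% are 30 × 0.10 × 0.204 = 0.61 to 30 × 0.10 × 0.280 = 0.84.

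**Size, lens exchange.** The only figure is in section 1.1: "Only one patient out of 127 had the IOL explanted because of glare and haloes". Applied to 30 patients, 30/127 = 0.24 exchanges are expected, and the chance of at least one is 1 − (126/127)³⁰ = 0.21. The figure is for another lens, with no follow-up period stated, so it is not a rate before Visit 3.

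**What the study must deliver.** Section 4.6.1 plans descriptive statistics, and section 4.7 calls the study a pilot. No test, effect size or precision target is stated that a shift of this size could breach.

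**The case for a change.** The strongest reply is that the visit schedule belongs to the protocol, that a measurement not taken cannot be recovered, and that one sentence bringing the Visit 3 tests forward would secure it. The point about recovery stands. So does the fact that section 3.4.2 (withdrawal) does not mention re-intervention and that no unscheduled visit is described.

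The small figures also depend on the assumed rate. If 10% of all patients, and not 10% of the eyes above 1.0 D, were re-treated before Visit 3, 3 of 30 would be expected, with a 96% chance of at least one. If those were 3 LRI eyes at the modelled average above 1.0 D (0.396/0.280 = 1.41 D), the LRI mean would fall by 0.10 × (1.41 − 0.25) = 0.116 D, slightly more than one standard error. So the effect is not negligible under every assumption. But nothing in the protocol points to such a rate within that window, and 1-month autorefraction would still show the state before any later procedure.

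Nor would the extra sentence be a clear gain. It would replace 3-month values by earlier ones in selected eyes, and section 1.1 says of incisions that "there is a tendency for regression of the effect during the first 9 months after surgery". An early reading could therefore flatter LRI eyes. The questionnaire compares the two eyes, so it could not be completed as designed if a procedure were agreed before second-eye surgery.

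**Conclusion.** The concern does not hold. The reading of the schedule is correct, but the protocol states nothing wrong and contradicts nothing here. Section 4.8 sets out a commitment to patients and does not place a procedure before Visit 3. How re-treated eyes enter the summaries can be left to a statistical analysis plan, which is not shown.

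Under the assumed repair of 2-10% of eyes above 1.0 D, the shrinkage is 0.003-0.030 D. At 10% it is about 0.17-0.31 of a standard error with eyes independent, and fewer than one LRI eye is affected. These sizes rest wholly on assumed means, spread, threshold and rates; a much higher early rate would raise them. The conclusion rests first on the text and on the descriptive, pilot purpose of the study. Followed as written, the plan yields sound descriptive results. A rule for early re-intervention would be an optional contingency with a drawback of its own, and leaving it out is not an error.
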